
Two hours after ingestion of NAC/placebo, participants will undergo the post-treatment imaging studies. We chose to begin scanning 120 minutes after NAC and 90 minutes after TRYp, because 1) our preclinical data show that NAC administered 30 minutes prior to TRYp administration attenuates KYNA production through KAT II inhibition; 2) our preliminary data suggests that peripheral kynureine and KYNA levels are initially elevated 30 minutes after TRYp ingestion, and continue to increase over the next three hours and remain elevated for at least 3.5 hours; 3) NAC pharmacokinetic studies have demonstrated that peak serum levels occur within 90-150 minutes of administration and remain elevated for 4-6 hours (46,48); and 4) GSH, an indirect measure of NAC in the CNS, starts to elevate 50 minutes after NAC administration, reaches maximal elevation 90-110 minutes after oral NAC administration and remains elevated for at least 120 minutes (49). Thus, there should be sufficient time to complete the post-treatment MRI, clinical, laboratory, and cognitive assessments. A non-blind pharmacist will dispense all study medications. The blind will be broken

only if a medical emergency requires this information. If this occurs, the participant will be withdrawn from the study. The day after each challenge day, the RA will follow-up with the participant, via telephone, to evaluate whether there are any persistent effects from the receipt of the challenge medications. Any concerns of the participant will be reported immediately to the study physician.

Procedures/Assessments	Evaluation Phase (2 weeks)	Challenge Visit #1:	Challenge visit #2:	Initials
Informed Consent, Evaluation to Sign Consent	X			
Medical Screening: Medical History, physical exam, blood draw, urinalysis, toxicology screen, pregnancy test (females), EKG, medication use screening, caffeine use screening, Birth Control Selection (females)	X			
MRI screening	X			
Clinical Stability Determination (for participants with schizophrenia or a related disorder only): 2 unchanged CGIs	X			
Scheduling of challenge day visits	X			
Participant arrival at Brief Stay Unit (BSU) Review of Study Procedures		7:15 am	7:15 am	
Urine pregnancy (females); expired CO**; urine toxicology and breath alcohol testing		7:30 am	7:30 am	
Insertion of heparin lock		7:40 am	7:40 am	
Vital signs, SEC, SSS;		7:50 am	7:50 am	

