Laboratory Assessments (1): kynureine pathway metabolites, inflammatory markers, oxidative stress and other related markers				
Nicotine Break (1)*		7:55 am	7:55 am	
Protein Free Snack				
Cognitive Measures (1): MCCB measures: HVLT-R, BACS Symbol Coding, BVMT, CPT-IP, WMS®-III, LNS;		8:00 am	8:00 am	
Clinical Assessments (1): BPRS, SANS, CDS, CGI		8:45 am	8:45 am	
Neuroimaging Studies (1)		9:15 am	9:15 am	
Nicotine Break (2)		10:30 am	10:30 am	
Oral Administration of N-acetylcysteine (NAC) 140 mg/kg up to a maximum of 15gm or placebo		10:35 am	10:35 am	
Oral Administration of Tryptophan 6 grams		11:05 am	11:05 am	
Lunch		11:25 pm	11:25 pm	
Vital signs, SEC, SSS		12:05 pm	12:05 pm	
Laboratory Assessments (2)				
Neuroimaging Studies (2)		12:20 pm	12:20 pm	
Laboratory Assessments (3)		1:35pm	1:35pm	
Protein Free Snack		1:40 pm	1:40 pm	
Nicotine break (3)				
Cognitive Measures (2)		1:55 pm	1:55 pm	

Clinical Assessments (2)		2:40 pm	2:40 pm	
Vitals, SEC, SSS		3:05 pm	3:05 pm	
Laboratory Assessments (4)				
Participant discharged. If participant has not returned to pre-challenge baseline, they will be reassessed every 30 minutes until ready		3:15 pm	3:15 pm	

*Nicotine breaks are optional and subject to occur at different times as long as they do not occur within 60 minutes prior to the neuroimaging studies.

**Due to the COVID-19 pandemic, the expired CO breathalyzer assessment is an optional procedure.

Randomization and Blinding: This will be a double-blind, placebo-controlled, randomized cross-over challenge study. Participant randomization will use a permuted block randomization system (block sizes 2 or 4), in which treatment assignment order is random within each block, with an equal number of participants assigned to each treatment, to generate a list of treatment assignments. Thus, it will be difficult to ascertain the next treatment assignment, even if a participant becomes unblinded, while any imbalance in the number of participants between the treatment groups will be kept within tight limits. All raters, investigators and other staff will be blind to treatment assignment except for the research pharmacist. The research pharmacist does not participate in assessing any of the primary symptom or side effect dependent variables and conveys no information about treatment assignment to participants or staff except in a medical emergency.

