In Exploratory Aim 2, we will evaluate whether the baseline KYNA and/or KMO activity levels can moderate the NAC effects in the Specific Aims 1-3 and Exploratory Aim 1. For the measurements in the Specific Aims 1-3, the interaction term between baseline KYNA and/or KMO activity and NAC treatment will be tested for the moderation effect. To examine whether baseline KYNA and/or KMO activity moderate the mediation pathways in Exploratory Aim 1, the nonparametric statistical inference (e.g. permutation tests and bootstrap inference) will be used due to relatively small sample size for the complex mediation and moderation model.

Potential Risks to the Participants:

Risks Related to N-acetylcysteine:

- Diarrhea. Somewhat likely and seriousness varies. If participants experience diarrhea they are free to end participation and may remain at the Research Center until they feel well enough to drive or someone can take them home. They will be instructed to drink fluids to remain hydrated.
- Flatulence. Somewhat likely and not serious. If participants experience flatulence they are free to end participation and may remain at the Research Center until they feel well enough to drive or someone can take them home.
- Nausea. Somewhat likely and not serious. If participants experience nausea they are free to end participation and may remain at the Research Center until they feel well enough to drive or someone can take them home.
- Vomiting. Somewhat likely and seriousness varies. If participants experience vomiting they are free to end participation and may remain at the Research Center until they feel well enough to drive or someone can take them home. They will be instructed to drink fluids to remain hydrated.
- Abdominal discomfort. Somewhat likely and not serious. If participants experience abdominal discomfort they are free to end participation and may remain at the Research Center until they feel well enough to drive or someone can take them home.
- Dysgesia. Not likely and not serious. If participants experience a change in their sense of taste they are free to end participation in the study and stop taking the study medication.
- Dizziness. Not likely and not serious. If participants experience dizziness they are free to end participation and may remain at the Research Center until they feel well enough to drive or someone can take them home.

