- Rash (with or without fever). Not likely and not serious. If participants experience a rash, with or without fever, they are free to end participation and may remain at the Research Center until they feel well enough to drive or someone can take them home.

Risks Related to Tryptophan:

- Nausea, dyspepsia. Somewhat likely but not serious. In our previous experience with tryptophan, nausea was seen in 1 of 11 participants exposed to tryptophan. The participant vomited and then felt relief. If participants experience nausea they are free to end participation and may remain at the Research Center until they feel well enough to drive or someone can take them home.
- Vomiting. Somewhat likely and seriousness varies. If participants experience vomiting they are free to end participation and may remain at the Research Center until they feel well enough to drive or someone can take them home. They will be instructed to drink fluids to remain hydrated.
- Sleepiness. Somewhat likely and not serious. If participants experience sleepiness they are free to end participation and may remain at the Research Center until they feel well enough to drive or someone can take them home.
- Transient exacerbation of cognitive impairment and/or exacerbation of schizophrenia symptoms. Expected, not serious. We hypothesize a small, transient decrease in cognitive testing scores or worsening of schizophrenia after participants receive tryptophan. This impairment is on the order of magnitude one would expect when sleepy or distracted and will not impact any routine functioning. All participants are evaluated by trained medical staff prior to discharge to confirm a return to baseline. Any persisting symptoms or abnormal vitals will be reported to the study physician who will determine whether the participant is safe to be discharged. A return to baseline before discharge will be recorded in the participant's study documents.

Blood Draw:

- Infection or bruising at the blood draw site. Not likely, seriousness varied. The blood draw and IV catheter placement will be done by experienced nursing staff using universal precautions.

MR Scanning:

- Claustrophobia. Not likely, not serious. Participants will be screened prior to scanning. They can also abort the scanning procedure by squeezing a rubber signal ball. Research staff will be in communication with participants throughout the scanning.

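### No checklist is assigned to the next-day call, so side effects that start after discharge and resolve before it may be missed or captured only unsystematically

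*Combined protocol and SAP*

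**What the plan says.** The Procedures/Assessments table gives both challenge visits the same clock. The row "Oral Administration of N-acetylcysteine (NAC) 140 mg/kg up to a maximum of 15gm or placebo" is at 10:35 am and the row "Oral Administration of Tryptophan 6 grams" at 11:05 am. The SEC is scheduled at 7:50 am, 12:05 pm and, in the row "Vitals, SEC, SSS", 3:05 pm. Discharge is at 3:15 pm, with this condition: "If participant has not returned to pre-challenge baseline, they will be reassessed every 30 minutes until ready".

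The Challenge Phase section, explaining when scanning starts, says of NAC that "peak serum levels occur within 90-150 minutes of administration and remain elevated for 4-6 hours". It says that kynurenine and KYNA are raised 30 minutes after tryptophan, go on rising for three more hours, and stay raised for a minimum of 3.5 hours. No upper limit is given.

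The same section provides for a call by the research assistant on the day after each challenge "to evaluate whether there are any persistent effects from the receipt of the challenge medications". The next sentence sends any concern the participant has to the study physician at once.

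Medical and Safety Assessments describes the SEC as 32 rated items plus three free spaces, and presents it as covering the effects already reported with NAC and tryptophan. It does not say that the SEC is used on the call, and it gives no recall period.

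**The concern.** Structured collection stops while the study compounds may still be acting, and the next planned contact has a narrower stated purpose. Diarrhea, vomiting, rash, sleepiness or a worsening of symptoms could begin at 5 pm and settle by morning. Such an episode is not persistent when the call is made, and no checklist prompts for it. Whether it enters the data depends on the participant mentioning it.

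The Randomization and Blinding section counts side effects among the dependent variables, so these are study data. Under Importance of the Knowledge to be Gained, the NAC dose is described as more than five times that of other clinical studies. The risk section calls sleepiness after tryptophan somewhat likely and a transient worsening of cognition or symptoms expected. Everyone who returns for the second challenge receives tryptophan again. At stake is how complete the first-day side-effect counts are. A later analysis cannot recover events that nobody asked about.

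**Working it through.** The plan states no figure for this point. The check is clock arithmetic on the Procedures/Assessments table, set against the pharmacokinetic statements in the Challenge Phase section.

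**Inputs.** NAC or placebo 10:35 am; tryptophan 11:05 am; last scheduled SEC 3:05 pm; discharge 3:15 pm; NAC peak at 90-150 min and elevation for 4-6 h; kynurenine and KYNA raised for a minimum of 3.5 h after tryptophan.

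**Time from dosing to the last SEC and to discharge.**
- NAC to last SEC: 3:05 pm − 10:35 am = 4 h 30 min.
- Tryptophan to last SEC: 3:05 pm − 11:05 am = 4 h 00 min.
- NAC to discharge: 3:15 pm − 10:35 am = 4 h 40 min.
- Tryptophan to discharge: 3:15 pm − 11:05 am = 4 h 10 min.

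**NAC elevation, counted from dosing.**
- Lower end: 10:35 am + 4 h = 2:35 pm. The last SEC comes 0.5 h after this.
- Upper end: 10:35 am + 6 h = 4:35 pm. The last SEC comes 1.5 h before this, and discharge 80 min before it.

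**NAC elevation, counted from the peak.** This is an assumption; the wording allows it but does not say so.
- Lower end: 1.5 h + 4 h = 5.5 h after dosing, 4:05 pm. The last SEC is 1.0 h earlier.
- Upper end: 2.5 h + 6 h = 8.5 h after dosing, 7:05 pm. The last SEC is 4.0 h earlier.

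**Kynurenine and KYNA.** The documented rise runs to 0.5 h + 3 h = 3.5 h after tryptophan, that is 11:05 am + 3.5 h = 2:35 pm. The last SEC is 30 min after that and discharge 40 min after. Since 3.5 h is a minimum, the plan does not say whether levels have fallen by discharge.

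**Interval without a checklist.** The time of the call is not given. Assuming it falls between 9 am and 5 pm, the interval from 3:05 pm is 17 h 55 min to 25 h 55 min, or about 18 to 26 h.

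**Exposure.** 100 participants × 2 visits = up to 200 challenge days. The NAC timing concerns only the NAC days, at most 100. Tryptophan, and the lack of a checklist on the call, concern all of them.

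**What could catch a late, short-lived event.**
- The 30-minute reassessments deal with effects already present at discharge, not with later onset.
- The call is described in terms of persistence, and beyond that relies on what the participant volunteers.
- The 7:50 am SEC at the second challenge visit comes at least two weeks later with no stated recall period, and the second visit has no such follow-up.

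None of the three is a specified, systematic way to record the event.

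**The case against.** The strongest reply is that the plan is more open than a quick reading suggests. A reader might infer that the call asks about nothing but persistent effects and that late events are therefore lost. The text does not say so: no call script is given, no limiting word is used, and any concern is passed on. A resolved episode can be reported. For the same reason, the documents do not support an inference that the study physician and the DSMB would not see events from the rest of the first day. What remains is that such reporting is spontaneous, whereas the on-site collection uses a checklist.

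The pharmacokinetic argument is also limited. A reader might take the 6 h figure alone and conclude that a fixed part of the NAC window goes unobserved. At 4 h from dosing there is no gap, the last SEC is well past the stated peak, and the figures were given to justify scan timing. This objection stands, so the point rests mainly on the uninstrumented call.

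The plan also says that this NAC dose has long been used in acetaminophen poisoning and has extensive safety data. No aim estimates side-effect rates, and SEC timing is identical under NAC and placebo. These points lower the stakes but do not fill the gap. Participant instructions may exist on consent pages that were removed, so they cannot be judged here.

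Finally, a reader might see conflicting discharge rules. The table's reassessment condition, the tryptophan risk text naming the "study physician who will determine whether the participant is safe to be discharged", and the option that participants "may remain at the Research Center until they feel well enough to drive or someone can take them home" read largely as one process. The pre-discharge evaluation is stated for all participants, and the option for those who stop early does not waive it. Nor is variation between sites an issue: challenge days run at a single unit.

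**Conclusion.** The point holds in a limited form. As written, the plan specifies no systematic collection of side effects that begin after discharge and resolve before the next-day call. They may be missed or captured only unsystematically, and first-day counts may be too low in both conditions. The documents give no rate for such events, so the size of the undercount cannot be stated, and the direction of any effect on the NAC-placebo difference is unknown.

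In time, the last SEC is 4.5 h after NAC and 4.0 h after tryptophan. Relative to the end of documented NAC elevation counted from dosing, it lies between 0.5 h after and 1.5 h before. This assumes that the table times are kept and treats serum level as a rough proxy for when side effects occur. The lack of a checklist on the call does not depend on either assumption.

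**What to change.** At the existing next-day call, administer the existing SEC for the whole interval since the last on-site SEC. Include events that have already resolved, record onset and end time for each item, and add a question on symptom worsening. Send new or worsened items to the study physician as well as whatever the participant raises. Report side effects by condition with this interval included, and say in the protocol that the call covers it.

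The cost is a few more minutes per call, on up to 200 calls, and some protocol wording. Reported rates will be somewhat higher, and should be presented so that on-site and post-discharge events can be told apart.

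An optional wording point: make explicit that the pre-discharge evaluation under Risks Related to Tryptophan also applies to participants who stop early under the risk sections. How this is done is for the sponsor to decide.
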